7.1. Inclusion criteria

- Aged 2-2.5 years
- Live in Tower Hamlets
- Caregiver willing to provide written informed consent.

7.2. Exclusion criteria

Children will be excluded if:

- The caregiver does not provide written informed consent.
- The child is not able to stand for an accurate height measurement.

7.3 Clinical sub-study inclusion and exclusion criteria

Clinical sub-study children will be included in this analysis if they were part of the clinical sample identified as having a growth disorder at [name] clinic, and where consent can be obtained from the parent/carer and from the patient if the child patient is now over 16 years old.

8. Study design

We will enrol a longitudinal cohort of 630 children to an observational study in which weight and height will be measured as part of standard care by a Health Visitor in the community. Enrolment and baseline research data collection will be at age 2.0-2.5 years, which coincides with a current contact point with Health Visitors. Parental height will also be measured at this visit (or reported height recorded if measurement is not possible). Prior to the visit, parents will complete the standard pre-school developmental assessment sent to all households by the Health Visitor (Ages and Stages Questionnaire; ASQ-3), and the informed consent form will request

permission to record these data for research purposes. A subgroup of 150 children will be offered a developmental assessment by a psychologist as a gold-standard comparison with the parent-reported ASQ-3. A follow-up height measurement for all children will be conducted by the health visitor approximately 6-12 months later as part of an extra preschool visit which is to be piloted in Tower Hamlets. If this is not operational by the time the study starts, the follow-up measurements will take place at the preschool booster vaccine appointment at the child's GP surgery, which also occurs at age 3.0-3.5 years. If this measurement is missed for any reason, health visitors will attempt to measure the child at a community/ children's centre or at home on a separate occasion. Children will also have their height and weight measured as part of the existing NCMP programme at school entry (age 4-5 years). Additionally, parents will be invited to monitor their child's height through use of an app, if they own a smart phone, which can provide additional data-points between age 2-4 years.

Using this approach, we are maximising opportunities to measure child growth at preschool ages by using existing contact points with health visitors and GP surgeries, and providing parents with the opportunity to measure their child's height using a novel smartphone app. Longitudinal height measurements, together with data collected on parental height, will be offered up to an automated growth-screening algorithm that we have developed using existing national datasets. Children with the most severe growth faltering (bottom 2-3% of children) will be identified and their caregivers/parents contacted to offer them referral to the paediatric endocrinology service at the Royal London Hospital for investigation of medical disorders of growth ([name]).

9. Study procedures

Children will be identified from the central health visitor lists held by the Health Visiting team at the Tower Hamlets GP Care Group (GPCG), which is a federation of 36 General Practices in Tower Hamlets and a partner in Tower Hamlets Together, a local integrated care partnership. From these lists, children will be randomly selected, with replacement, in two groups: i) the main growth study (N=480), and ii) the growth and development sub-study (N=150), for a total of 630 children. Group 1 will only undergo growth screening, and group 2 will additionally have a gold standard child development assessment conducted at baseline.

9.2 Screening

Prior to the 2.0-2.5 year contact, children's health visitors will contact the family to provide preliminary information about the study and explain that a PIS will be included with the ASQ-3 questionnaire that is routinely sent to families at this age. The health visitor will offer a follow-up phone call, video call or home visit to check the family received the PIS, to address any initial queries and to gauge their interest in the study. They will be offered a screening and consent visit to coincide with the

child's planned 2-2.5 year assessment (section 9.2). At this visit, the child will be screened by a health visitor against the inclusion and exclusion criteria to determine eligibility. Caregivers of eligible children who are interested in joining will be asked to provide written informed consent as outlined in section 9.3. Using demographic information from the primary care platform (EMIS), the information will be communicated in the main language spoken by the caregiver.

9.3 Informed consent

Informed consent will be taken by the study health visitor in a confidential setting (within a children's centre or the child's house) using e-consent on the REDCap database, which includes the questions on the study informed consent form (Form 4). If necessary, consent can be taken on paper using the same form and will still be considered valid. This will take place either prior to the first measurement/development assessment at age 2-2.5 years or on the day of this assessment. An electronic signature will be taken; in addition to a tick box and declaration, permitted forms of electronic signatures will include a stylus or finger drawn signature or a typed name. The health visitor will explain all study procedures, risks and benefits and confidentiality considerations. The study health visitor will explain that the project involves two assessments by health professionals, 6-12 months apart (one at the 2-2.5 year health visitor contact and one undertaken either by the GP surgery at the preschool booster immunisation appointment, or by the health visitor). In addition, as per standard care all children will have their development assessed by the health visitor using the parent-reported ASQ-3 assessment. Parents will also be invited to download a smartphone app and to measure their child's height at 3 timepoints, each time on the same day as the child's height is measured by a health professional (health visitor, GP practice nurse, school nurse). Caregivers will also be asked for consent to health visitors' collection of data on past medical history from children's primary care records and linkage of any relevant diagnoses or medications to the children's study data. It will also be made clear that there will be data linkage with the NCMP programme through Tower Hamlets Local Authority, which involves sharing identifiers (NHS number) if they are happy to provide consent for this to occur. Caregivers can opt out of this data linkage and their child can still be included in the internal study. Caregivers will be made aware that they will be provided with the child's growth measurements and a summary of their growth pattern, and that children with severe growth failure will be contacted and referred to the paediatric endocrinology service, and children with significant developmental concerns will be referred for further assessment through existing NHS referral pathways. In addition to data entry onto the NHS system, the caregivers will be made aware that their child's anthropometric and developmental data, and the parental heights will be recorded in a research database (REDCap) by the health visitor. Caregivers will be asked for consent for routine clinical data collected in the clinic (such as any diagnoses made by the endocrinologist) to be linked with the child's data in the study. [name] is a member of the study team and

leads the paediatric endocrinology clinic to which the children will be referred, and will enter any relevant clinical data onto the REDCap database.

Sub-studies

Development sub-study

A randomly selected subset of 150 children will also be invited to an additional appointment with a child psychologist for a detailed developmental assessment, which is not part of standard care; children in this sub-study will be enrolled using a separate consent form (Form 5). The caregiver will be asked to provide written informed consent and to keep a copy of the PIS. The primary caregiver must have parental responsibility to provide consent. Assent will not be sought since all children will be between 3 and 4 years old.

Where the developmental assessment suggests the child may be experiencing developmental delay, the study psychologist may share the Griffith's report with the child's Health Visitor with the parent's permission. Reports will not be generated for all children and will only be generated when concerns are identified. The Griffith's assessment result is not a formal diagnosis but can provide extra context for a clinician.

Qualitative sub-study

Following the first contact, we will invite a subgroup of participants in the study (caregivers) and health visitors working in Tower Hamlets to take part in focus groups. A total of 16 caregivers will be selected from the sample of children participating in the study to participate in two focus groups of between 6 and 8 participants. Caregivers participating in focus groups will be consented using a separate PIS (PIS 16) and consent form (Form 14).

We will also conduct one focus group with health visitors. A total of eight health visitors currently working within the Healthy Child Programme in Tower Hamlets will be sampled with the help of the health visiting team at the Tower Hamlets GPCG. Separate PIS and consent forms will be used for health visitors (PIS 17, Form 14).

Clinical sub-study secondary analysis

A separate clinical sample of children with diagnosed growth disorders will be analysed to test the algorithm and obtain optimal cut offs for growth screening. In order to obtain a height measurement previous to the child's first attending growth clinic, we will seek to link the children's clinical data to their NCMP height measurement (measured at school and recorded by NHS England at 4 or 5 years old).

We will seek retrospective consent from the child's parent/carer and, in cases where the child is over 16 years old, from the child patient themselves. Consent will be obtained electronically using a e-consent form through REDcap (Forms 22 and 23).

Unique secure links will be sent to patients or their families via email, after first sharing an electronic copy of the PIS (PIS 24 and 25).

9.4 Schedule of study interventions The study schedule is shown in Table 1.

Baseline (age 2-2.5 years)	Qualitative research sub-study	Development sub-study ²	Follow-up (age 2.5-3.5 years) ³	NCMP measurement
Screening for eligibility (Form 3)	Informed consent (Form)	Child development – GMDS	Height measurement (child)	Height measurement
Informed consent (Form 4)	Qualitative interview/ focus group (Form 12)	Informed consent (Form 5)	Height measurement (parental)	Weight measurement
CRF_1 baseline questionnaire			School enrolment information / SENCO input	CRF_2 endline questionnaire
Height measurement				
Weight measurement				
Parental height ¹				
Child development (ASQ-3)				

¹Attending parent's height (s) measured (where possible) or estimated height documented if not attending

²Children in the development sub-study will have all baseline procedures conducted in addition to the developmental assessment conducted by a psychologist

³Conducted either by the GP at the time of pre-school vaccinations or the health visitor through a home visit

The following study forms will be used to capture data or provide information:

Form name	Details	Administered by
Patient Information Sheet – growth study (Form 1)	Detailed information about what the study is about and what participation involves	Health visitor
Patient Information Sheet – growth and development study (Form 2)	Detailed information about what the study is about and what participation involves (including additional developmental assessment)	Health visitor
Screening form – inclusion and exclusion (Form 3)	Initial check that child lives in study catchment area and there are no exclusion criteria	Health visitor
Consent form for growth study (Form 4)	Signed by caregiver if informed consent given	Health visitor
Consent form for growth and development sub- study (Form 5)	Signed by caregiver if informed consent given	Health visitor
Baseline form (Form 6)	Baseline data form includes height, weight, development and demographics. No identifiers.	Health visitor

Identifiers/contact form (Form 7)	Form with patient identifiers and contact details	Study team
Follow-up form (Form 8)	Follow-up data form includes height, weight, development. No identifiers.	Health visitor/ psychologist
Exit form (Form 9)	Used if caregiver wishes to withdraw from the study.	Health visitor
Referral form (Form 10)	Template to write to participant's GP asking to refer to paediatric clinic.	PI
NCMP linkage form (Form 11)	Identifiable information to submit to Tower Hamlets Local Authority to link to NCMP data.	Study team
Focus groups – qualitative research sub- study discussion guide – caregivers (Form 12)	Guidance for moderators of the focus groups of caregivers.	Study team
Focus groups – qualitative research sub- study discussion guide – health visitors (Form 13)	Guidance for moderators of the focus groups of health visitors.	Study team
Focus groups – caregivers. Consent form (Form 14)	Signed by caregiver if informed consent given	Study team
Focus groups – health visitors. Consent form (Form 15)	Signed by health visitor if informed consent given	Study team
Focus groups – caregivers. Information sheet (Form 16)	Detailed information on the purpose of the sub- study and what participation involves	Study team

Focus groups – health visitors. Information sheet (Form 17)	Detailed information on the purpose of the sub- study and what participation involves	Study team
Evaluation questionnaire (caregivers) – 2.5-3.5 years (Form 18)	Evaluation questionnaire for all caregivers to be completed after the 2.0- 2.5 year and the 2.5-3.5 year contacts	Study team (completed by caregiver)
Evaluation questionnaire (caregivers) – end of study (Form 19)	Evaluation questionnaire for all caregivers at the end of the study (after the 4-5 year contact)	Study team (completed by caregiver)
Evaluation questionnaire – caregivers – smartphone App (Form 20)	Evaluation questionnaire for all caregivers regarding use of the Smartphone App	Study team (completed by caregiver)
Evaluation questionnaire - health visitors (Form 21)	Evaluation questionnaire for all health visitors participating in the main growth study	Study team (completed by health visitor)
Clinical sample linkage consent form for carers/parents (Form 22)	Consent form for clinical sample NCMP linkage	Study team (completed by patient or caregiver)
Clinical sample linkage consent form for patient aged 16 or over (Form 23)	Consent form for clinical sample NCMP linkage	Study team (completed by patient or caregiver)
Clinical sample linkage information sheet for carers/parents (Form 24)	Information leaflet for clinical sample NCMP linkage	Study team
Clinical sample linkage information sheet for patient aged 16 or over (Form 25)	Information leaflet for clinical sample NCMP linkage	Study team

Baseline visit (age 2.0-2.5 years):

At the baseline visit, data will be collected using CRF1 (Baseline visit). Demographic data will be collected from the caregiver. Caregivers will be asked to have the personal child health record (Red Book) available, from which will be transcribed: birth weight and length (if available) and any previous measurements of height, weight and head circumference. We will also collect data on gestation and growth on antenatal scans, feeding difficulties including any previous interventions from dietetics or paediatrics, chronic health conditions and any hospital attendances/admissions. The child's height will be measured to the nearest 1mm using a stadiometer according to an SOP. The child's weight will be measured to the nearest 100g using a stand-on scale according to an SOP. The accompanying parents will have height measured using the same methods; if either parent is absent, an estimate will be made of their height based on parental recall. If both parents are not present (i.e. the child is cared for by different family member), we will attempt to contact the parents to record their reported heights. If the child is not in contact with their biological parents, we will not make further attempts to contact family members and will record this as missing data. Health visitors will support caregivers to download a smartphone growth application and demonstrate how to use it. Caregivers will be invited to take the first smartphone measurement at this point. The app converts height data from the camera image to a numerical figure, and this will be transferred to a secure central server with additional relevant demographic data (e.g. gender, ethnicity, weight, date of birth and parents' heights) and an anonymous identifier in GDPR-approved secure space. Each participant will have an anonymised unique identifier. No patient images / names will be transferred. The smartphone app has existing ethical approval (IRAS project ID: 286683; REC reference: 21/WM/0032).

Follow-up visit 2.5-3.5 years

Children will have a further height measurement at approximately 3.0 years by the health visitor. If the preschool health visiting contact is not operational at the time, the child will instead have their height measured by the nurse/healthcare assistant administering the immunisations at the preschool booster appointment at their GP practice, or at a planned research visit appointment Through the health visitor contact at 3.0 years children will have a repeat developmental assessment using the ASQ-3 questionnaire. Data will be collected using **CRF 2 (Follow-up visit).** Child height will be assessed using the same tool as at baseline. If there are any missing parental heights a further attempt will be made to measure or record an estimated height. Families will be occasionally contacted by the study team by phone to improve retention in the study and to remind caregivers about the smartphone app.

School entry measurement (age 4-5 years)

Child height and weight will be recorded as part of the routine NCMP programme at school entry (4-5 years of age). We will provide identifiers to Tower Hamlets Local Authority to enable them to link the NCMP measurement to enrolled children and provide us with their heights and weights recorded at 4-5 years of age. This is a

feasibility piece to see if data could be used from NCMP in a larger screening programme. We will also collect data on school enrolment, and screen for educational concerns by health visitors screening school nursing notes to review if there has been any input from a special educational needs co-ordinator at school. After the NCMP measurement, we will distribute questionnaires for caregivers and health visitors to collect data on feasibility and acceptability of the study procedures. We will also conduct focus groups with small groups of participants (see below).

At each of the 3 measurements of height we will identify the 2-3% of children with the poorest growth, as categorised by the algorithm (based on parental height, child height, and child growth velocity), in whom prior studies show a high prevalence (30-40%) of medical disorders. We will contact parents of these children to offer referral to the paediatric endocrinology clinic at the Royal London Hospital. A member of the study team will call the parents to inform them and will write to the child's GP to request a referral into the Royal London Hospital clinic via the e-referral system. We will evaluate acceptability and feasibility of the screening and referral process, using parental and primary care staff questionnaires. We will evaluate uptake by calculating the proportions screened, referred, investigated in clinic and diagnosed with medical disorders. At the clinic, children will be assessed by a paediatric endocrinologist and will undergo routine medical evaluation for short stature, with appropriate follow-up.

Development sub-study (age 2.0-2.5 years):

A random sample of 150 children will also be invited to enrol in a sub-study to generate pilot data on the sensitivity of the parent-reported ASQ-3 to assess child development compared to a gold standard development battery, the GMDS, undertaken by a psychologist. These children will undergo a neurodevelopmental assessment during their routine health visitor visit of their motor, cognitive, language and social skills using a standardized test battery (GMDS) by a child psychologist. Using data from the ASQ-3 developmental assessments conducted at baseline and follow up visits by the health visitor, we will investigate relationships between growth and development and assess content validity of the ASQ-3 by comparing it with the GMDS.

[figure not shown]
Qualitative sub-study (following the 2-2.5 year visit)

We will also invite a subgroup of participants in the study (caregivers) and health visitors working in Tower Hamlets to take part in focus groups. We will convenience sample 2 focus groups of 6-8 caregiver participants, with language interpretation if appropriate. With support from the Child Growth Foundation and using our own experience of qualitative research with families of children experiencing stunting in sub-Saharan Africa we will raise and explore generative questions with the focus groups. We will convene the focus groups following the first contact to gather qualitative data on acceptability of the study procedures (in addition to questionnaires). We will also convene a separate group of 6-8 health visitors working in Tower Hamlets to discuss child growth and development monitoring and referral pathways. We will transcribe the data and generate coding categories to analyse with NVivo software.

Flowchart of study procedures

Clinical sample secondary analysis

A sample of ~200 children with diagnosed growth disorders will be linked to NCMP data and used to test the performance, sensitivity and specificity of the growth screening algorithm. Retrospective consent will be sought from the patient and their parent/carer to link their clinical data to their NCMP height measurement. The patients NHS number, diagnosis, age at diagnosis and parental heights will then be shared with NHS England (data controllers for NCMP). Here, data will be linked to NCMP measurements. We will also seek consent to share the patient's first name, surname, postcode and date of birth with NHS England to link the data in cases where the NHS number is missing from the NCMP dataset. Data will be pseudo-anonymised by removing NHS numbers or other identifiers and generating random ID numbers before being shared with the Office for Health Improvement and Disparities (OHID) at the Department of Health and Social Care.

[figure not shown]
Data will be analysed in-house at OHID according to data sharing agreements between OHID and NHS England, and to minimize the sharing of personal data. The data analysis plan has been developed by researchers at QMUL and analysis will be conducted collaboratively, although data will not be shared outside of OHID at this stage. The growth-screening algorithm will be applied to NCMP data to determine the children's standardized height for age and sex as well as the distance from their mid-parental heights. We will use an age-matched sample of children participating in the Born in Bradford study as controls. We will assess the sensitivity and specificity of using different cut-offs to find children with an underlying growth disorder. We will also estimate the potential improvement in age at diagnosis when using the screening algorithm by calculating the mean of the subtracted age at NCMP measurement from the true age at diagnosis for the children who were correctly identified as having a growth disorder by the algorithm. Analysis will be conducted using Stata 17. Aggregated results will then be shared with researchers at QMUL.

This sub-study will run parallel to the main pilot study, and as it uses a separate dataset is not included in the flowchart of study procedures. A flowchart of the linkage procedure is shown below.

Flow diagram of data sharing and linkage procedure for clinical sample secondary analysis

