9.5 Follow-up procedures

Participants who have short stature for their age and parental heights will be identified using the screening algorithm at baseline. These participants will be referred for further clinical investigation. At follow-up, growth velocity will also be included in the screening algorithm, and any children found to have reduced growth velocity will be referred. Children will be followed up in a dedicated research clinic within Barts Health NHS Trust. [name] clinic is an established paediatric endocrine/growth clinic at the Royal London Hospital. Children will be seen and assessed as per standard clinical practice. They will have auxological assessment (height, weight, head circumference and recording of parental heights), a clinical review (history and physical examination). Patients requiring further investigations for short stature will follow a current best practice guideline investigation protocol. More detailed genetics (if a specific genetic disorder is suspected), Growth Hormone testing (as per standard departmental protocols) or referral to another speciality (e.g. gastroenterology) may be requested if clinically indicated.

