We will employ an algorithm based on previous methodology, using variables individually and in combination, after checking for co-linearity. Different cut-off values will be chosen and the proportion of the population judged to have linear growth failure estimated for each cut-off. We will then examine the detection rate for each cut-off by applying it to data from ~200 local children treated in the specialist paediatric endocrinology centre with known growth disorders e.g. Growth Hormone Deficiency (GHD), Turner Syndrome (TS) and Small for Gestational Age without catch-up growth (SGA). Consent will be obtained retrospectively from these patients and their parents/carers to link their routinely obtained clinical data (diagnosis, age at diagnosis, height and parental height) to previously height data obtained at school entry via the NCMP. To do this linkage, the hospital clinical data (and the associated NHS number or other identifiers) will be shared with NHS England. This will allow us to calculate sensitivity-and-specificity algorithm cut-offs for the detection of these conditions. This will enable a trade-off between detection rate (sensitivity) and the false positive rate (1-specificity) to be evaluated. Additionally, the time elapsed from the first abnormal screening result until the clinical diagnosis of growth hormone deficiency will be related to the cut-off values.

The outcomes for Aim 1 are age of identification of stunting (which will be reported but the study is not powered to detect age of diagnosis); feasibility of measuring children in the community; the percentage of children referred; the percentage of children found to have underlying medical conditions; and the feasibility, acceptability and inter-test variability of a smartphone app and stadiometer height measures.

The algorithm will be applied to measures collected from each child at each visit, with children who are identified by the algorithm as being in the bottom 2% for height or

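### The estimated gain in age at diagnosis allows no time between a screening flag and a diagnosis, so it is overstated for children diagnosed after the school measurement

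*Protocol*

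**What the plan says.** Protocol section 9.4, Clinical sample secondary analysis, names the target: "We will also estimate the potential improvement in age at diagnosis when using the screening algorithm". It then fixes the estimator: "calculating the mean of the subtracted age at NCMP measurement from the true age at diagnosis for the children who were correctly identified", meaning those whose disorder the algorithm flags. The sample is about 200 children with a known diagnosis, linked to their first NCMP height at age 4 or 5.

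The pathway after a flag is described elsewhere in the protocol:

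- Section 9.4, School entry measurement: "A member of the study team will call the parents to inform them and will write to the" child's GP, who is asked to refer through the e-referral system. At the clinic, "children will be assessed by a paediatric endocrinologist and will undergo routine medical evaluation for short stature, with appropriate follow-up".
- Section 9.5: "Patients requiring further investigations for short stature will follow a current best practice guideline investigation protocol". This may include "Growth Hormone testing (as per standard departmental protocols) or referral to another speciality".

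No section gives the length of this pathway, and the sub-study formula does not subtract it. Section 10.2 (Aim 1) describes a closely related quantity in neutral terms: "the time elapsed from the first abnormal screening result until the clinical diagnosis of growth hormone deficiency will be related to the cut-off values".

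**The concern.** An improvement in age at diagnosis is the age at diagnosis without screening minus the age at diagnosis with screening. The sub-study puts age at measurement in the second place. The first term, the child's actual age at diagnosis, already contains the referral and work-up time of routine care. The second contains none. The comparison is therefore not like for like, and among children diagnosed after NCMP the error always favours screening. A child whom routine care would have diagnosed within the screening delay is credited with a gain although screening would have brought none.

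The synopsis (section 4) names age at diagnosis of medical disorders as the primary outcome of the larger study for which this work is to support a grant application. The pilot cohort expects only 4-5 diagnoses. An estimate from about 200 diagnosed children is therefore likely to carry weight in planning, and an inflated gain could lead to an optimistic effect assumption there.

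**Working it through.** The protocol states no numerical result for this quantity, so there is no figure to reproduce. The check is algebraic, with assumed values to show the size.

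**Definitions.** Let A be true age at diagnosis, N age at NCMP measurement, D = A − N, and L the time from flag to diagnosis on the screening route. A, N and the formula come from section 9.4. That L is greater than zero follows from the steps in sections 9.4 and 9.5. Its length is not given.

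**The two quantities.**
- Protocol estimator: mean(D).
- Age at diagnosis by the screening route: N + L. The difference from actual age at diagnosis is A − (N + L) = D − L.
- A child diagnosed sooner by routine care loses nothing from being screened, so the child's gain is max(0, D − L).

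**Error for one child**, reported value D against gain max(0, D − L):
- D at least L: excess is D − (D − L) = L. Example with D = 3 and L = 0.5 years: reported 3, gain 2.5, excess 0.5.
- D between 0 and L: excess is D, which is less than L. Example with D = 0.3 and L = 0.5: reported 0.3, gain 0, excess 0.3.
- D below 0 (diagnosed before NCMP): reported value is negative, gain is 0, so the estimator is too low for that child.

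**Size among children with D > 0.** Assume D is gamma-distributed with mean m and standard deviation s, so shape k = (m/s)² and scale s²/m. With S_k the survival function for shape k at that scale, the mean gain is m·S_{k+1}(L) − L·S_k(L). The overstatement is m divided by the mean gain, minus 1.

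| Mean D (SD), years | Delay 3 months | Delay 6 months | Delay 12 months |
|---|---|---|---|
| 4.5 (2.5) | gain 4.250, +6% | gain 4.000, +12.5% | gain 3.506, +28% |
| 3.0 (2.0) | gain 2.751, +9% | gain 2.505, +20% | gain 2.043, +47% |
| 1.5 (1.2) | gain 1.258, +19% | gain 1.041, +44% | gain 0.695, +116% |

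In the last row, 19% and 42% of children gain nothing at delays of 6 and 12 months. Every mean, SD and delay here is an assumption, and so is the gamma shape.

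**Effect of children diagnosed before NCMP.** Suppose 30% of the children averaged were diagnosed on average 2 years before NCMP, the rest have mean D of 2 years (gamma, shape 2), and L = 0.5 years. The protocol mean is 0.7 × 2 − 0.3 × 2 = 0.80 years. The mean gain among the 70% is 1.52 years by simulation, so over all children it is 0.7 × 1.52 = 1.06 years. Here the protocol's figure is too small.

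**The case against.** The wording is hedged: the gain is called potential, and the text says exactly what is subtracted from what. Section 4 says the pilot is not designed to test whether age at diagnosis falls, section 10.2 says it is not powered for this, and the primary endpoint is feasibility and acceptability. Section 9.4 also refers to a data analysis plan, not shown here, which might contain a delay adjustment. All of this lowers the importance. None of it makes the stated formula measure what it is called: the protocol does not describe the figure as a maximum, and the objection is to an estimator it fixes, not to detail it leaves out.

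A reader might infer several stronger claims that the documents do not support:

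- *Every flagged child's gain is too large by the full delay.* A child diagnosed within the delay is overstated by less. Section 7.3 does not exclude children diagnosed before NCMP, and they pull the mean down. Section 9.3 shows that a height taken before first clinic attendance is intended, but no rule enforces it.
- *The present figure is an upper bound on the gain from the programme.* Besides negative intervals, the piloted programme also screens at 2-2.5 and 2.5-3.5 years. A child flagged then could gain more than a calculation from the school-entry height alone can show.
- *This is the only information on age at diagnosis.* Section 10.2 also reports the age at which each condition is identified in the pilot and compares it with the average age at diagnosis. If identification there means diagnosis in clinic, that comparison already includes the delay.
- *The pilot will supply the delay.* Diagnoses are to be linked to study data, but no section says that a flag date is recorded.

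**Conclusion.** The point stands in limited form. For children diagnosed after their NCMP measurement, the stated estimator exceeds the gain in age at diagnosis by the screening-route delay, or by the whole interval where that is shorter. The direction for those children follows from the protocol's text. The size does not: it depends on an interval and a delay that the documents do not give. Over the assumed range it runs from about 6% (mean interval 4.5 years, 3-month delay) to 116% (mean 1.5 years, 12-month delay). Net overstatement of the reported mean is likely if, as intended, nearly all heights precede first clinic attendance, but the text does not guarantee it. This is a correction to a secondary analysis and leaves the primary endpoint untouched. It is worth making because it is cheap and the figure may be carried into a larger study.

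**What to change.** In section 9.4, Clinical sample secondary analysis:

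1. Rename the present quantity 'time from NCMP measurement to diagnosis'. State that, among children diagnosed after the NCMP measurement, it is the maximum gain from screening at NCMP alone.
2. For those children, report the gain as max(0, age at diagnosis − age at NCMP − delay) for fixed delays of 3, 6 and 12 months. Age at diagnosis and age at measurement are already in the linked dataset (sections 9.4 and 13.1), so this can be run where the data are held.
3. If flag and diagnosis dates are captured in the pilot, show the observed flag-to-diagnosis interval as supporting information only. With 4-5 diagnoses expected, reached through referrals made by the study team, it cannot fix the delay.

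The cost is a few lines of text, one extra calculation, and a less favourable figure than the present formula gives for these children. No new data are needed for items 1 and 2.
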